6.5 Safety Assessments

Emergency services (e.g., a crash cart) will be available within the hospital in case of any acute adverse reactions. AEs will be monitored during the entire procedure. Specifically, the patient will be monitored with non-leading questions to monitor the patient for the occurrence of transient side effects that are described below.

6.5.1 Risks/Benefits Assessment.

The known risks from the administration of Definity are minimal. Definity is well tolerated and has been used extensively in echocardiography applications. A total of 1716 subjects were evaluated in pre-market clinical trials of Definity. Of these patients 144 (8.4%) reported at least one treatment-related adverse reaction. The most common AEs were reported in the Central and peripheral nervous system (3.1%), Body as a Whole (2.4%) and Gastrointestinal system (1.8%). The most common events were headache (2.3%), back and renal pain (1.2%), flushing (1.1%) and nausea (1.0%). All of the non-serious reported side-effects have been transient, usually lasting only a few minutes.

There were 26 serious AEs and 15 (0.9%) subjects discontinued because of an AE. Nineteen (1.1%) suffered serious cardiopulmonary adverse events including eight deaths. The deaths occurred several days after Definity administration and appear to be related to the course of underlying disease. Of the 11 other serious AEs, which appeared within days of the drug administration (2-15 days), all appeared to be a progression of underlying cardiac and non-cardiac disease. However, a role for Definity in the initiation or course of these AEs cannot be ruled out. As a result of post market analysis, the FDA added a black box warning to Definity in 2008 for patients with unstable cardiac or respiratory conditions. In one of the largest retrospective multicenter study evaluating the effect of Definity administration in 66,164 cases, no deaths were reported attributable to the drug use [Wei et al. 2008]. The rate of severe allergic reactions for either cardiac or abdominal ultrasound imaging following Definity was 0.0006% [Wei et al. 2008]. It was concluded that the severe AE rate following the use of ultrasound contrast agents is no greater and may be lower, than the reported event rate for other contrast agents used in other cardiac imaging studies [Wei et al. 2008].

A prospective, open-label, nonrandomized, multicenter phase 4 surveillance registry was conducted at 15 clinical sites in the USA to assess the risk for adverse cardiopulmonary events during or within a 30 minute period after administering Definity to patients between February 2008 and April 2009 [Weiss et al. 2012]. In this study, 1053 patients were administered Definity and no deaths, serious AEs and other significant AEs were reported [Weiss et al. 2012]. The overall drug related adverse event rate was only 3.5% and within these cases, 96.5% of the AEs were of mild or moderate intensity [Weiss et al. 2012]. Based on study by Weiss et al [2012], the FDA concluded that deaths or serious AEs are “unlikely to occur at a rate of more than 0.3% when Definity is used according to recommendations” [FDA 2011].

The use of an intravenous needle and the fluids given through the needle may cause minor discomfort, bleeding under the skin (bruise), and possible infection at the site of needle insertion.

Clinically significant adverse effects from the administration of Definity are unlikely. The use of contrast with the new ultrasound imaging techniques is expected to provide significantly more information than conventional ultrasound techniques. This may lead to a non-invasive method for characterization of adnexal masses.

To minimize and/or eliminate risks a nurse will be present during the entire procedure. Emergency services (e.g., a crash cart) will be available within the hospital in case of any acute adverse reactions. Adverse events will be monitored during the entire procedure.

The risk benefit ratio is low. Based on the available nonclinical and clinical safety data and the anticipated dose levels of Definity that will be used in this study, safety concerns are minimal. The potential side effects related to Definity administration are described above and listed in greater detail in the investigator's brochure.

6.6.2 Adverse Events

An AE includes any condition that was not present prior to trial treatment, but appeared following initiation of trial medication; any condition that was present prior to trial treatment, but worsened during trial medication; or any condition, of which the subject has a history, that was not present prior to trial medication initiation but reappeared following administration of Definity. This would include conditions that are likely to be associated with an underlying or intermittent disease (e.g., angina, flu, etc.).

The subjects will be monitored for AEs during the entire procedure. All AEs, including observed or volunteered problems, complaints, signs or symptoms, and diagnoses, occurring from the initiation of

Definity dosing until the completion of the Definity administration will be recorded on a serious or non-serious AE data form, whether or not associated with the use of the trial medication. GE Healthcare will be informed of all AEs. In addition all unexpected and serious AEs are reported to the TJU IRB and to the FDA. The investigator is required to submit all unexpected and serious AEs to the TJU IRB within 48 hours, and to GE Healthcare. Fatal AEs related to treatment which are unexpected must be reported within 24 hours to the TJU IRB and to GE Healthcare. Fatalities not related to the study drug/device must be reported within 5 days. The PI of the study has previous experience running ultrasound clinical trials and will serve as the study sponsor. He will be responsible for ensuring all FDA requirements are met and all AE are properly reported.

The AE forms will include: subject identification number and initials; subject's date of birth, gender, and ethnicity; name of the institution, date of Definity administration; signs/symptoms and severity; date of onset; date of resolution or death; relationship to the study drug; action taken; concomitant medication(s) including dose, and route and duration of treatment.

Whenever possible, the AE will be evaluated and reported as a diagnosis rather than individual signs and symptoms. If a definitive diagnosis is not possible, the individual signs and symptoms will be recorded. The investigator(s) will evaluate and note the duration, intensity, and relationship to (association with) the Definity administration, the action taken, and the determination of seriousness for each AE.

INTENSITY OF AEs

The intensity of the AE will be characterized as mild, moderate, or severe.

Mild AEs are usually transient, require no special treatment, and do not interfere with the subject's daily activities.

Moderate AEs traditionally introduce a low level of inconvenience or concern to the subject and may interfere with daily activities but are usually ameliorated by simple therapeutic measures.

Severe AEs interrupt a subject's usual daily activity and typically require systemic drug therapy or other

treatment.

When the intensity of the AE changes over time, the maximum intensity will be recorded.

RELATIONSHIP TO DEFINITY ADMINISTRATION

The relationship or association of the AE to the Definity administration will be characterized as "unlikely," "possible," or "probable." A relationship assessment will be performed by the investigator to determine if an AE is attributable to Definity and will be recorded on a data form. The investigator will refer to the Definity investigator brochure for assistance in determining AE relationship.

An "unlikely" relationship indicates that there is little or no chance that Definity caused the reported AE; other conditions, including concurrent illnesses, progression or expression of the disease state, or a reaction to a concurrent medication, appear to explain the reported AE.

A "possible" relationship indicates that the association of the AE with Definity is unknown. However, the AE is not reasonably attributed to any other condition.

A "probable" relationship indicates that a reasonable temporal association exists between the AE and Definity administration and, based upon the investigator's clinical experience, the association of the event with the trial medication seems likely.

SERIOUS ADVERSE EVENTS

A serious AE is defined as a significant clinical hazard, contraindication, or precaution that:

- Results in death
- Is life-threatening (In the opinion of the investigator, there is an immediate risk of death from the AE as it occurred. This does not include an AE that had it occurred in a more serious form may have caused death.)
- Results in a persistent or significant temporary disability/incapacity defined as a substantial disruption of a person's ability to conduct normal life functions
- Results in or prolongs an existing in-patient hospitalization (an overnight stay in the hospital, regardless of length) [Note: A hospitalization for an elective procedure or treatment which is

- not associated with an AE, hospitalization for a pre-existing condition which did not worsen, and hospitalization for reasons of convenience or observation, do not constitute an serious AE.]
- Is a congenital anomaly/birth defect (in offspring of a subject taking the trial medication, regardless of time to diagnosis)
- Is an important medical event that may not result in death, be life-threatening, or require hospitalization but based upon the appropriate medical judgment, the event may jeopardize the subject and may require medical or surgical intervention to prevent one of the outcomes listed for the definition of a serious adverse experience.

The designated medical monitor will review all serious and unexpected adverse events associated with the protocol and provide an unbiased written report of the event within 10 calendar days of the initial report. At a minimum, the medical monitor will comment on the outcomes of the adverse event and relationship of the event to the Definity administration. The medical monitor will also indicate whether he concurs with the details of the report provided by the principal investigator.

A copy of the serious AE will be retained on file with the respective subject's data forms.

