6.3 Trial Assessments

6.3.1 Medical History

A full demographic profile, known drug allergies or intolerances, and a review of the subject’s medical/surgical history will be recorded. If the woman is of childbearing potential, she will have a urine pregnancy test (the results of which will be made available to the subject prior to study initiation). Emergency services (e.g., a crash cart) will be available within the hospital in case of any acute adverse reactions. Adverse events will be monitored during the entire procedure.

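### Section 6.6.2 requires AE forms only for events up to the end of the Definity administration, although AEs are monitored for the whole procedure

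*Combined protocol and SAP*

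**What the plan says.** Section 6.6.2 contains four statements that bear on this point.

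- Monitoring: "The subjects will be monitored for AEs during the entire procedure".
- Recording, in the next sentence: all AEs from the start of "Definity dosing until the completion of the Definity administration will be recorded on a serious or non-serious AE data form", whether or not linked to the drug.
- Definition: an AE includes a new condition after trial medication starts, a worsening, or a past condition that "reappeared following administration of Definity". No end point is given.
- Reporting: "In addition all unexpected and serious AEs are reported to the TJU IRB and to the FDA". No onset limit is given here either.

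Whole-procedure monitoring is repeated in section 6.3.1 ("Adverse events will be monitored during the entire procedure"), in section 6.5 ("AEs will be monitored during the entire procedure") and at the end of section 6.5.1.

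Section 3.1 limits participation to one imaging study of about an hour. Section 6.7.1 counts participation as complete once both doses and the imaging are done.

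Section 6.5.1 summarises the pre-market experience: "The deaths occurred several days after Definity administration and appear to be related to the course of underlying disease". It continues: "Of the 11 other serious AEs, which appeared within days of the drug administration (2-15 days"). It adds that a role for the agent could not be excluded.

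**The concern.** Two consecutive sentences set different windows. Subjects are watched for the whole procedure, but the required record stops when the administration stops. A mild reaction that begins during imaging after the infusion would be seen, yet the rule does not require it to be written down. No separate reporting duty covers it if it is non-serious and expected.

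The recording sentence also governs the serious AE form. A serious event that starts later must be reported to the IRB and the FDA, but the text does not say that it goes on the form, and it describes no step for finding it.

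What is at stake is the completeness of the safety record in an off-label use (sections 1.1 and 5). A count of few or no AEs is harder to interpret if the rule stopped counting before observation stopped. The plan has no safety hypothesis, and no efficacy result depends on this.

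**Working it through.** The plan gives no figure to reproduce. The check compares the windows and then asks what sizes can be derived.

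**1. Windows side by side**

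| Item | Starts | Ends | Section |
|---|---|---|---|
| AE definition | first trial medication | not stated | 6.6.2 |
| Monitoring | procedure | end of procedure | 6.3.1, 6.5, 6.5.1, 6.6.2 |
| Required AE form | first dosing | end of administration | 6.6.2 |
| Reporting of serious and unexpected AEs | not stated | not stated | 6.6.2 |

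The form window is the narrowest of the four, and no visible section extends it.

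**2. Length of the form window**

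Inputs: a 15-minute pause between doses and a nominal 5-minute infusion (section 6.3.2); 25 ml of saline plus up to 1.5 ml of agent, run at 4 to 10 ml/min (section 6.2).

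- Window from the bolus = pause + infusion time. Nominal: 15 + 5 = 20 min.
- Infusion time over the rate range: 26.5/10 = 2.7 min to 26.5/4 = 6.6 min, so the window is about 18 to 22 min.
- Section 3 gives 30 minutes between doses instead of 15. With 30 the window is about 33 to 37 min. The two intervals contradict each other and must be reconciled separately; this conclusion does not depend on which applies.

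In every case the required record ends 0 min after the infusion. The registry cited in section 6.5.1 observed for 30 min after dosing.

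**3. The part of the visit left outside the record**

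This cannot be computed. The visit takes about an hour (section 3.1), but that hour includes baseline imaging before dosing and is not divided. Section 6.3.2 places the reperfusion imaging after the infusion in one phrase, but describes 3-4 minutes of equilibrium enhancement, which would fit imaging during a 5-minute infusion.

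**4. Events after the visit**

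Inputs from section 6.5.1: 11 serious AEs at 2-15 days; 1716 subjects. Assumptions: one event per subject, and the same rate in this trial.

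- Rate: 11/1716 = 0.64%.
- Expected in 45 subjects: 45 × 0.00641 = 0.29.
- Chance of at least one: 1 − (1 − 0.00641)^45 = 25%.

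The rate is probably too high for this trial. The 11 events appeared to reflect progression of underlying disease, and section 4.2 excludes unstable cardiopulmonary conditions. The range is therefore 0 to about 0.3 events, most likely none.

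**The case against.** The strongest reply is that the recording sentence sets a minimum. It says what will be recorded and does not forbid recording more. The AE form has separate fields for the date of administration and the date of onset, and the second adds little if every recordable event starts during dosing. The sentences on evaluating each AE and judging its relationship to the agent carry no time limit. This stands as far as it goes: an investigator could record more than the rule requires. The requirement still ends with the infusion, and completeness should not rest on discretion.

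Second, the gap within the visit may be negligible if imaging overlaps the infusion, and section 6.5.1 describes non-serious effects as brief. The first part stands and limits the size. The second concerns how long effects last, not when they start.

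Third, the team is not cut off from subjects afterwards. Section 4 draws them from a co-investigator's own surgical patients, and section 6.4 has the lesion marked at excision and pathology, staging and markers collected from clinical care. So there is a plausible informal route by which later events reach the team. That weakens the concern about later serious events, but it is not a stated step for finding AEs.

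Fourth, section 6.5.1 also quotes a regulatory conclusion that deaths or serious AEs are unlikely to exceed 0.3%. That gives 45 × 0.003 = 0.14 events. It supports a small number, but the registry behind it observed only 30 minutes after dosing and so says little about later onset.

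The package insert, the investigator's brochure and the text under Appendix A, heading F (roles and responsibilities) are not in the copy reviewed. They might state further duties.

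**Conclusion.** The mismatch holds. As written, a non-serious AE that starts after the infusion but within the monitored visit is outside the required record. Later serious or unexpected AEs are reportable if they become known, but no visible section sets a formal step to look for them. Any error is toward too few recorded AEs; its size cannot be computed, is probably small and may be zero. The figure of about 0.3 late serious events in 45 subjects rests on carrying a pre-market rate into a population with stricter exclusions.

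Three stronger readings do not follow:

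- A reader might infer that later AEs may not be recorded, or that late serious AEs go unreported. The text neither bars later recording nor limits the reporting duty by onset.
- A reader might divide the 11 late events by the 19 subjects with serious cardiopulmonary events and infer that 58% of such events would be missed here. Section 6.5.1 calls the 11 events, not subjects, and links them to cardiac and non-cardiac disease. The ratio would describe historical cases, not the AEs this trial would fail to record.
- A reader might see the open-ended AE definition, or the duty in Appendix A to list all AEs in the final report, as flat contradictions of the recording rule. They differ in scope only.

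**What to change.** Reconcile the monitoring and recording statements. In section 6.6.2, replace the end point in the recording sentence (completion of the administration) with an end of AE recording no earlier than the end of the monitored imaging procedure. Add that any serious AE with onset after first dosing that becomes known to the team is entered on the serious AE form. This costs a wording change in the protocol and in any AE form instructions, and adds no visit time.

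Optional and secondary: use the records already collected around the scheduled surgery to check once for serious AEs. This costs up to 45 record checks, and it will bring in some unrelated events that then need a relationship assessment. Any longer observation or recording period is for the sponsor to set.

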6.3.2 Ultrasound Imaging

The ultrasound examinations will be performed by a qualified sonographer. Procedures and equipment for this trial will be used in accordance with typical clinical procedures. All trial procedures will be conducted in accordance with Good Clinical Practice. A modified Logiq E9 scanner with a [REDACTED] C10-3v EV transducer

(GE Healthcare) operating in SHI mode will be used to obtain subharmonic radiofrequency (RF) data from the adnexal mass within the ovary and/or fallopian tube. Both the experimental machine and software will be labeled as an investigational device with a GE provided label prior to beginning any clinical experiments (21 CFR 812.5).

A baseline grayscale ultrasound scan of the lesion will be obtained and the following criteria assessed: the size, shape, and orientation of the site; echogenicity compared to surrounding tissue. Standard PDI of the mass will also be performed to select the area with the greatest vascularity. The distribution of color signals and the overall color content of the mass will be evaluated by comparing the pattern and amount of color to normal tissue on the contra-lateral side. If uniform, the color will be categorized as less intense, iso-intense or more intense than normal tissues. If non-uniform, the color will be described by location, intensity and distribution. Anastomoses between adjacent vessels will be noted (as 1-2, 3-5 or >5 vessels connecting). The vascular pattern will also be graded as peripheral, radial, spotty or a combination. Digital clips of the two baseline imaging modes will be acquired.

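### Adverse-event causality is rated only against Definity and recording is limited to the dosing period, although the SHI scanner is also investigational and a fatality rule refers to drug or device

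*Combined protocol and SAP*

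**What the plan says.** Section 6.3.2 describes a modified scanner with an endovaginal transducer running in SHI mode and states: "Both the experimental machine and software will be labeled as an investigational device with a GE provided label". The trial therefore exposes women to an investigational imaging system as well as to an off-label contrast agent.

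Section 6.6.2 ties causality to the agent. The only relationship item listed for the AE form concerns the study drug, and the investigator's evaluation of each AE covers its association with Definity. The rating scale opens "The relationship or association of the AE to the Definity administration will be characterized as" and gives three levels, each defined by reference to Definity or the trial medication. Under Serious Adverse Events, the medical monitor must comment, as a minimum, on the "relationship of the event to the Definity administration".

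The reporting rules in the same section use other terms. The 24-hour rule covers unexpected fatal AEs related to treatment, a word the section does not define. The slower rule reads: "Fatalities not related to the study drug/device must be reported within 5 days".

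On timing, the AE definition begins with "any condition that was not present prior to trial treatment, but appeared following initiation of trial medication", and its other two limbs also refer to trial medication or Definity. AEs are recorded from the start of Definity dosing until its administration is complete. Section 6.6.2 also has subjects monitored for AEs throughout the procedure, as do Sections 6.3.1, 6.5 and 6.5.1. Section 6.5.1 names procedural risks: "The use of an intravenous needle and the fluids given through the needle may cause minor discomfort", followed by bruising and possible infection at the needle site.

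**The concern.** Two gaps appear when the safety rules are set against the design.

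The first is attribution. An AE caused by the probe, the scan or the SHI exposure can be recorded, but no specified step asks whether the device or procedure caused it. The fatality rules need that judgement, or something close to it, and the specified forms do not collect it.

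The second is capture. The cannula is placed, and the baseline grayscale and power Doppler scan is done, before the first dose. An event that first appears then, or after the infusion ends, is outside the recording rule even though staff are told to watch for it.

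At stake is how clear a safety account the pilot can give of endovaginal SHI when a larger study is planned. The diagnostic and correlation results are not affected.

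**Working it through.** The plan gives no figure on this point and no formula applies, so the check is a comparison of the stated rules.

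**1. What is under study (6.3.2, 7.2.1).** The scanner and software are investigational, and all three hypotheses concern SHI performance.

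**2. What each causality step rates (6.6.2).**
- AE form: relationship to the drug.
- Investigator's evaluation of each AE: relationship to Definity.
- Scale, definitions and reference brochure: Definity.
- Medical monitor: Definity, as a minimum.

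None of these steps rates the device, the SHI mode, the endovaginal procedure or IV placement.

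**3. Where a recognised probe injury lands on the scale.** 'Possible' excludes events reasonably attributed to another condition. 'Probable' requires a likely association with the medication. 'Unlikely' remains, and on a Definity-only scale that is the correct score. The device cause simply has no field. Harm from ultrasound acting on circulating microbubbles involves Definity and could be scored 'possible' or 'probable'.

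**4. What the reporting rules need (6.6.2).**
- Unexpected and serious AEs: to the IRB within 48 hours, with no relatedness condition.
- Unexpected fatal AEs related to treatment: within 24 hours.
- Fatalities unrelated to drug or device: within 5 days.

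If an unexpected death is put down to the device and not to Definity, the 24-hour rule applies only if treatment includes the device, which the text does not settle. The 48-hour rule applies either way. For such a death the ambiguity is therefore between 24 and 48 hours. An unexpected death unrelated to either comes under both the 48-hour and the 5-day rule, and the section does not say which prevails.

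**5. What the recording window covers.** The sequence in 6.3.2 is baseline scan, bolus, pause, infusion.
- Before the window: cannula placement and the baseline endovaginal scan.
- Inside it: bolus, pause and infusion.
- After it: anything first appearing once the infusion ends. A needle-site infection would probably show itself only then.

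As a rough guide, a 15-minute pause (6.3.2) plus a 5-minute infusion gives 15 + 5 = 20 minutes, out of about one hour for the imaging protocol (3.1). With the 30-minute gap given in Section 3 it is 30 + 5 = 35 minutes; those two passages need reconciling. This describes time covered, not share of risk, and the conclusion does not depend on it.

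**6. Comparison with the monitoring statements.** Monitoring spans the procedure, while recording spans dosing. As written, an event can be observed without being recordable.

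**The case against.** The strongest reply is that Section 6.6.2 already has safeguards that do not depend on attribution. Events inside the window are recorded whether or not they are associated with the medication. GE Healthcare, the scanner manufacturer, is told of all AEs. Unexpected and serious AEs go to the IRB and FDA regardless of cause. The form also holds signs, severity, onset and action taken. All of this stands, and it limits the point. It does not supply the missing rating, and it does not reach events outside the window.

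A reader might infer that the trial could not report a device-related AE at all, or that the count of such events is bound to be zero. The documents do not support that: the events are recorded and forwarded, and an untabulated category is not a zero count. An upper confidence limit for no events in 45 women would add nothing either, because Section 7.2 plans no AE-rate estimate.

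A reader might also infer that nobody could make the device judgement. The monitor's remit is a minimum, so a device comment is allowed. The form's field list is not stated to be exhaustive. The text under Appendix A, heading F (roles of study personnel) is not in the copy reviewed. The supportable statement is that no rule available for review requires the judgement.

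Finally, the AE definition turns on when a condition appears and is worded as inclusive, so a cannula bruise first seen during dosing qualifies. It is also fair that the stated objectives are diagnostic and that the documents give no evidence of harm from the probe or SHI. The tighter limit is the recording window.

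**Conclusion.** The concern holds in limited form. Every specified causality step addresses Definity alone, while the scanner and software are investigational and the fatality rules refer to drug or device and to an undefined treatment. Separately, the recording window omits events first appearing at cannula placement, during the baseline endovaginal scan or after the infusion, which conflicts with monitoring throughout the procedure.

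The size is qualitative. In up to 45 women, device or procedure attribution would be missing from the specified forms, and out-of-window events would not have to be recorded. General AE reporting and the planned statistical results are unaffected. The conclusion assumes that the form carries no causality field beyond those listed and that the text not available under Appendix A does not assign a device rating. The gap is worth closing because these are explicit rules that, if followed, lose safety information on the imaging mode under study.

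**What to change.** - **Attribution:** add a second relatedness rating, on the same three levels, for the investigational SHI device and endovaginal procedure, including IV placement. Carry it through the AE form, the investigator's assessment and the medical monitor's report.
- **Window:** record AEs from cannula placement or first probe insertion, whichever is earlier, through the end of the whole study procedure and a stated period after the infusion. Align the AE definition in Section 6.6.2 with this. Moving only the start would still miss late events such as a needle-site infection.
- **Reporting rules:** reconcile the treatment and drug/device terms in the fatality rules so that both draw on the two ratings, and state how those rules relate to the 48-hour rule.

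The cost is one extra field, short wording changes, some follow-up after the infusion, and a few more mild procedural AEs such as bruising or probe discomfort. No imaging step or planned analysis changes.
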